## 5 Study Objectives

The primary, secondary, and exploratory objectives along with the associated endpoints as per the study protocol are presented as follows:

### ***Part A – Tumor Histology Agnostic***

#### **Primary Objective**

- To assess the clinical benefit of ulixertinib as measured by the overall response rate (ORR) in patients receiving ulixertinib that have advanced malignancies harboring a MEK or atypical BRAF alteration.

#### **Primary Endpoint**

- ORR will be defined as the percentage of patients achieving a Best Overall Response (BOR) of confirmed Complete Response (CR) and/or Partial Response (PR), according to RECIST 1.1.

#### **Secondary Objectives**

- To evaluate the safety profile of ulixertinib.
- To assess the duration of response (DOR).
- To assess the progression free survival (PFS) and overall survival (OS) over 18 months.
- To measure the blood levels of ulixertinib and selected metabolites.

#### *Secondary Endpoints*

- Safety profile, including term, incidence, severity, and duration of AEs, as per CTCAE v5.0.
- DOR according to RECIST 1.1.
- PFS time according to RECIST 1.1.
- OS time.
- Pharmacokinetic profile of ulixertinib (BVD-523) and selected metabolites.

#### **Exploratory Objectives**

- To evaluate the effects of ulixertinib on pharmacodynamic markers.

#### *Exploratory Endpoint*

- ctDNA, tissue biopsies, and/or blood to access biomarkers. Assays include, but are not limited to, phosphorylation of RSK from whole blood, RPPA to assess protein levels, e.g. DUSP 4/6, plus Nanostring and/or RNA-exome to assess mRNA expression in tissue pre- and post-ulixertinib treatment.

#### **Part B – Tumor Histology Specific**

##### **Primary Objective**

- To assess PFS in patients receiving ulixertinib in defined tumor histologies (up to three histologies to be selected) compared to physician's choice of treatment. Patient's tumors must harbor a specified MEK or atypical BRAF alteration.

##### *Primary Endpoint*

- PFS will be defined as the time from first day of trial medication to disease progression according to RECIST 1.1, or death.

##### **Secondary Objectives**

- To evaluate the safety profile of ulixertinib.
- To assess OS over 18 months in patients receiving ulixertinib with a defined tumor histology and specified MEK or atypical BRAF alteration, compared to physician's choice of treatment.

- To determine the ORR and DOR in patients receiving ulixertinib with a defined tumor histology and a MEK or atypical BRAF alteration, according to RECIST 1.1, compared to physician's choice of treatment.

#### *Secondary Endpoints*

- Safety profile, including term, incidence, severity, and duration of AEs, as per CTCAE v5.0.
- OS time.
- ORR and DOR according to RECIST 1.1.

## 6 Study Design

### 6.1 STUDY DESIGN AND POPULATION

This is a two-part, phase II, multicenter study of the ERK inhibitor ulixertinib (BVD-523) with an open-label, tumor histology agnostic part (Part A) and a tumor histology specific part (Part B).

#### ***Part A: Tumor Histology Agnostic***

[figure not shown]
Part A of the study will be open label and enroll patients to one of six groups based on their tumor alteration:

- *Group 1:* Patients with tumors, other than colorectal cancer (CRC), having a BRAF alteration that results in an amino acid change at positions G469, L485, or L597.
- *Group 2:* Patients with tumors, other than CRC, having a defined Class 2 BRAF alteration.
- *Group 3:* Patients with tumors, other than CRC, having an atypical BRAF alteration (non V600) that is not specified in Group 1 or Group 2.
- *Group 4:* Patients with CRC having any atypical BRAF alteration.
- *Group 5:* Patients with tumors, other than CRC, harboring alterations in MEK1/2.
- *Group 6:* Patients with CRC harboring alterations in MEK1/2.

#### ***Part B: Tumor Histology Specific***

Part B of the study will randomly enroll patients with one of up to three specified tumor histologies to receive either ulixertinib or the physician's choice of treatment in a 2:1 ratio. Tumors must harbor a specified MEK or atypical BRAF alteration. If a patient progresses on physician's choice of treatment, crossover to the ulixertinib arm is permitted.

An overview of the study design is presented in [Figure 1](#) below.

**Figure 1. Study Design**

Ongoing data from Part A will also be used to prioritize one or more tumor histologies that warrant study in Part B. The specific histologies and alterations to be included in Part B will be selected based on available data from Part A and discussion with the clinical investigators, the medical monitor, and the sponsor.

Part A of the study will enroll approximately 228 patients with 38 patients per group. Additional patients may be enrolled as appropriate. Part B of the study will enroll 80-100 patients per histology, with up to three histologies included, additional patients may also be enrolled.

The estimated duration of accrual is 21 months. The total duration of the study will be approximately 38 months.

Patients are considered to have completed the study if they have completed all phases of the study including the last visit or the last scheduled procedure.

Patients will continue on study therapy until documented disease progression, intolerable toxicity, study closure, or until other treatment discontinuation criteria is met. Patients who discontinue study therapy prior to disease progression, will continue to be followed for progression, survival or initiation of subsequent anticancer therapy for 18 months from the date of study therapy initiation. It is estimated that participants will be on study for up to 30 months.

Screen failures are defined as patients who consent to participate in the clinical trial but do not meet the criteria required for participation in the trial during the screening procedures. Patients who do not meet the inclusion criteria may be rescreened and will be assigned a new subject identification number.

## 6.2 STUDY TREATMENTS AND ASSESSMENTS

Patients will receive 600 mg oral doses of ulixertinib, which is to be taken twice daily (b.i.d.) orally for 28 days, at 12-hour  $\pm$  2 hours intervals, approximately the same time each day with food and at least 8 ounces of water. Patients will be provided the study drug for a full cycle to self-administer at home.

Patients experiencing unacceptable toxicity will have their treatment interrupted until the toxicity returns to  $\leq$  Grade 1 or pre-treatment baseline. Dose adjustments will be done in consultation with the investigators and medical monitor of the study. If a non-treatment related adverse event (AE) or toxicity-related dose delay lasts for  $>$  21 days, treatment will be discontinued permanently, and the patient will be removed from study treatment.

### 6.3 RANDOMIZATION AND BLINDING

Part A is designed as an open-label study. All patients in Part A will receive treatment with orally administered ulixertinib. Patients in Part B will receive either treatment with orally administered ulixertinib or the physician's choice of treatment in a 2:1 ratio. In Part B, if a patient progresses on the physician's choice of treatment then they may crossover to the ulixertinib arm.

Part B randomization will be performed as total enrollment rather than on a site basis.

Randomization/enrollment in both parts will be performed by using Interactive Voice/Web Response System (IxRS). In Part B, the IxRS will randomly assign the patient to one of the two treatment arms (ulixertinib or the physician's choice of treatment). In both parts, the IxRS will assign the patient a unique patient identification number. This patient identification number will then be reported on all eCRF pages and in any study documents.

### 6.4 SAMPLE SIZE JUSTIFICATION

#### *Part A*

Approximately 38 patients will be recruited into each group in Part A.

With 34 patients in a group and assuming the true ORR is 40%, there is approximately 80% power to reject the null hypothesis that the true ORR is  $\leq 20\%$  in that group, with a 1-sided alpha of 5%. Assuming a 10% drop out rate, up to 38 patients will be recruited in each group.

#### *Part B*

Part B sample size estimation may be updated after Part A results are available.

Approximately 80-100 patients will be randomized, using a 2:1 ratio, for each histology group in Part B.

Using a 2-sided, log-rank test with a 5% alpha, and assuming a median PFS of 1.7 to 8.5 months (depending on histology) in the physician's choice arm and twice as long on the ulixertinib arm, approximately 80 to 100 patients will be required in each group to achieve 80% power to show a statistically significant difference between the arms. This also assumes that each group will take approximately 24 months to accrue, and the analysis is expected to be performed 18 months following the last patient accrued. The anticipated loss to follow-up is estimated to be 10%.

## 7 Statistical Considerations

### 7.1 STUDY TREATMENT

The study drug is ulixertinib (BVD-523). The study treatment refers to treatment with ulixertinib (BVD-523). For Part B, the physician's choice treatment will be provided to patients in the comparator arm.

### 7.2 PLANNING OF ANALYSES

This SAP covers final analysis for Part A and Part B, although the analysis for Part B will be further described once Part A results are available in an updated SAP version. The planned timing of analysis for Part A is 18 months after the last patient enrolled starts treatment. Since Part B depends on Part A results it is not possible to estimate by when Part B analysis will occur. The SAP will be updated after Part A results are available and the Protocol is amended.

Given that the study was early terminated during Part A, an abbreviated CSR focusing on safety will be prepared. Therefore not all Tables, Listings and Figures planned in SAP version 1 will be required. The Shells table of contents will have an additional column to indicate which outputs will be delivered for the final analysis of Part A.

### 7.3 STUDY AND ANALYSIS PERIODS

Study periods are summarized in [Table 1](#) below. Analysis periods will mirror these periods and are summarized in [Table 2](#) below.

**Table 1. Study periods**

Period	Visit	Planned days
Part A and Part B		
SCREENING	Screening (up to 4 weeks before Baseline)	Day -28 to Day -1
TREATMENT	Cycle 1	Baseline Day 8 ± 3 Day 15 ± 3
	Cycle 2	Day 29 ± 3 Day 36 ± 3 Day 43 ± 3
	Cycle 3 – Cycle n	Day 57 ± 3 – Day n ± 3
FOLLOW-UP	End of Treatment (EOT) Visit	≤14 ± 3 days after last dose
	Safety Follow-Up	30 ± 3 days after last dose
	Follow-Up	Every three months (± 7 days) until death, end of the study, or patient withdrawal of consent, whichever comes first.

**Table 2. Analysis periods**

Phase	Period	Definition
Part A and Part B	PRE-TREATMENT	From informed consent form (ICF) signature to the day before first dose of study treatment.
	ON-TREATMENT	From the day of first dose of study treatment to ≤14 ± 3 days after last dose of study treatment (date of EOT visit), or the earliest date of subsequent anti-cancer drug therapy – 1 day, whichever occurs first.
	FOLLOW-UP	From day ≤14 ± 3 after last dose of study treatment, or the earliest date of subsequent anti-cancer drug therapy, whichever occurs first, to end of study. End of study is date of completion / discontinuation from the study as collected in the CRF or the last recorded assessment in the database if the patient has not completed/discontinued the study at the time of the analysis.

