- ^a Patients will return to the clinic or will be contacted for a safety follow-up assessment 30 days \pm 3 days after the last dose of study drug was taken; or earlier if subsequent therapy for advanced malignancy is initiated prior to 30 days \pm 3 days.
- ^b Patients or their legally authorized representatives will be contacted every three months (\pm 7 days) until death, end of the study, or patient withdrawal of consent, whichever comes first. Survival and subsequent treatment status may be collected by public records, medical records, or by contacting the patient or their legally authorized representative by phone.
- ^c Full medical history at screening, only review/update of history at subsequent visits.
- ^d Oncologic history of the malignancy under study including prior regimens (duration of therapy, best response on therapy, date of discontinuation, and reason for discontinuation), surgery, and radiation therapy.
- ^e Physical examinations should be symptom driven after the Screening Visit.
- ^f Ophthalmological examinations will be performed by an ophthalmologist at screening, and whenever clinically indicated. In Part B, only patients in the ulixertinib arm need an ophthalmological exam. See section 10.1.5 for a full description of tests.
- ^g ONLY if the screening serum pregnancy test was performed more than 1 day previously.

- h After screening and baseline, if urine pregnancy test is positive, confirm with serum test.
- i Visit 2 clinical lab samples should be collected pre-dose if not done during Screening Visit within 72 hours of start of treatment.
- j Chemistry, hematology, and urinalysis. After Cycle 2, clinical labs to be performed prior to starting each new cycle or more frequently when clinically indicated at the investigator's discretion. See section 10.1.6 for a full description of test.
- k Patients with a normal ECG in Cycle 1 do not need to have repeat ECGs in subsequent cycles. Patients should be supine for 5 minutes prior to the ECG.
- l Tumor assessments will be made prior to dose initiation, at Visit 5, and then every 2 cycles. Patients who discontinue treatment for reasons other than progression will have assessments at the EOT visit (unless their previous assessment was performed within 28 days). The same imaging modality used for an individual patient (i.e. CT or MRI) at Screening should be maintained throughout the study.

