### Summaries of baseline and change from baseline

Baseline and change from baseline will be calculated for all assessments, including additional assessments (if applicable), as follows:

- Baseline is defined as the last available assessment prior to first dose of study treatment, including additional assessments (where applicable). Assessments that occurred on the same day as first dose, when time of assessment is not available, will be assumed to be prior to first dose (unless the assessment is planned after first dose in the protocol).
- Change from baseline will be calculated as the difference between the post-baseline assessment value and the baseline value.

Whenever applicable, percent change from baseline will be calculated as the difference between the post-baseline assessment value and baseline value divided by the baseline value multiplied by 100.

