### 9.9.2 *Clinical Safety Laboratory Evaluation*

All haematology, biochemistry, and urinalysis laboratory tests collected will be reported.

The numerical measurements and change from baseline of all haematology, biochemistry, and urinalysis laboratory tests will be summarized using descriptive summary statistics for each visit.

For laboratory tests covered by the NCI-CTCAE (version 5), laboratory data will be graded accordingly. 'Normal' will be assigned for all non-missing values not graded as 1 or higher. For laboratory tests where grades are not defined by NCI-CTCAE, results will be graded by the low/normal/high classifications based on laboratory normal ranges as collected in the CRF. Separate tables will be created for Graded and Non-gradable laboratory values.

Haematology and biochemistry laboratory tests will be summarized by:

- Tables (Gradable and Non-gradable) to describe the worst on-treatment value by cycle.
- Shift tables (Gradable and Non-gradable) to compare baseline to the worst on-treatment value.

Listings of all laboratory data with values flagged to show the corresponding NCI-CTCAE grades and the classifications relative to the laboratory normal ranges will also be provided. Also results of serum pregnancy tests will be listed.

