### 9.9.3 *Other Safety data*

#### 9.9.3.1 *Vital signs*

Vital signs include the following parameters: systolic blood pressure (SBP) (mmHg), diastolic blood pressure (DBP) (mmHg), pulse (beats/min), and temperature (°C).

The numerical measurements and change from baseline of all vital signs parameters will be summarized using descriptive summary statistics for each visit.

Shift tables of baseline to worst on-treatment result (low, normal, high, very high) will be presented.

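### On-treatment starts on the calendar day of first dose, so a pre-dose Day 1 baseline also counts as on-treatment, and the shift tables cannot show improvement or missing follow-up for those patients

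*SAP*

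**What the plan says.** **Periods.** SAP 7.3, Table 2, ends the pre-treatment period the day before dosing: "From informed consent form (ICF) signature to the day before first dose of study treatment". The on-treatment period runs "From the day of first dose of study treatment to ≤14 ± 3 days after last dose of study treatment (date of EOT visit". Both limits are dates, not dose times. SAP Table 1 likewise lists the Baseline visit under the treatment period, Cycle 1: "Baseline Day 8 ± 3 Day 15 ± 3".

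**Baseline.** SAP 7.8: "Baseline is defined as the last available assessment prior to first dose of study treatment, including additional assessments (where applicable". A same-day assessment with no recorded time "will be assumed to be prior to first dose", unless the protocol plans it after the dose.

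**Shift tables.** SAP 9.9.2 asks for "Shift tables (Gradable and Non-gradable) to compare baseline to the worst on-treatment value", for haematology and biochemistry. SAP 9.9.3.1 asks for "Shift tables of baseline to worst on-treatment result (low, normal, high, very high) will be presented". SAP 7.7 and 7.8 add unscheduled and repeat data to the worst-value derivation. None of these sections, nor the shells, requires a post-dose value or removes the baseline record. The adverse-event definition in SAP 9.9.1 does carry an explicit after-first-dose limit.

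**Day 1 data.** Protocol 10.3.1.2 schedules vital signs for every patient at Visit 2, listed ahead of the first dose. For laboratory tests, Protocol Table 3.1, footnote i, reads: "Visit 2 clinical lab samples should be collected pre-dose if not done during Screening Visit within 72 hours of start of treatment".

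**Outputs kept.** Laboratory shift tables 14.3-2.3.1, 14.3-2.3.2, 14.3-2.6.1 and 14.3-2.6.2 and vital-sign shift table 14.3-3.2 are all flagged for the final analysis.

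**The concern.** A shift table compares a patient's state before treatment with the worst state afterwards. If the before value is also in the pool from which the after value is picked, the result can never be better than baseline and can never be absent. A patient with Grade 2 ALT before the first dose and only Grade 1 or normal values afterwards would be reported as 2 to 2, when the worst post-dose grade is 1. A dosed patient with no post-dose sample would appear as unchanged, when the correct entry is Missing.

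This matters because SAP 7.2 says the early-termination report will focus on safety, and because eligibility admits some abnormal baselines. Protocol 7.1 allows hemoglobin from 9.0 g/dL, and AST/ALT up to 3 times ULN (up to 5 times only with liver involvement by tumor).

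**Working it through.** The plan gives no figure to reproduce here. The check has three parts.

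**1. Is a pre-dose Day 1 value in both sets?**
- Pre-treatment ends the day before first dose (Table 2), so nothing dated Day 1 is pre-treatment.
- On-treatment begins on the day of first dose (Table 2), so everything dated Day 1 is on-treatment. A recorded clock time does not change this, because the limit is a date.
- A pre-dose Day 1 value, timed or untimed, is the last assessment before dosing and hence the baseline (SAP 7.8).

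The same record is therefore both the baseline and a candidate for worst on-treatment.

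**2. Which cells can be reached?** Let b be the baseline category and w the worst post-dose category.
- Rule as written: worst = max(b, w), or b if there is no post-dose value.
- Post-dose rule: worst = w, or Missing if there is none.

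For gradable tests (Normal and Grades 1 to 4, with a known baseline) there are 5 × 6 = 30 cells. As written, only cells with worst ≥ b occur: 5 + 4 + 3 + 2 + 1 = 15. The 10 improvement cells and 5 Missing cells are lost. The SAP does not rank Low against High, so for the other tables I assumed Normal < Low = High < Very High, with ties staying at baseline.

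| Table | Rule | Reachable | Improvement | Missing |
|---|---|---|---|---|
| Gradable laboratory | as written | 15 | 0 | 0 |
| | post-dose | 30 | 10 | 5 |
| Non-gradable laboratory | as written | 5 | 0 | 0 |
| | post-dose | 12 | 2 | 3 |
| Vital signs (four categories) | as written | 9 | 0 | 0 |
| | post-dose | 20 | 5 | 4 |

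The zeros do not depend on how ties are broken, since a move to Normal is blocked either way. Where w is worse than b, both rules return w, so worsening is unaffected. The laboratory shift shells print the improvement cells and a Missing column that the rule cannot fill. The body of the vital-sign shell is not shown, but SAP 7.8 provides a Missing category for tables in general.

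**3. How many patients?** The overlap exists only where the baseline is a Day 1 value.
- Vital signs: essentially all patients, since Visit 2 readings are scheduled for everyone.
- Laboratory tests: only patients whose screening tests were not done within 72 hours of treatment start, or who had a repeat on Day 1. The documents do not give that share.

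Illustration for systolic pressure, using SAP Table 7 (normal to 130, high 131–160, very high from 161 mmHg), high direction only, with no drug effect. The distribution is my assumption: mean 125, between-patient SD 14, within-patient SD 10 mmHg. The total SD is √(14² + 10²) = √296 ≈ 17.2, so the share above normal at baseline is P(Z > (130.5 − 125)/17.2) = P(Z > 0.32) ≈ 37.5%. Simulation gives the share whose post-dose values were all in a better category but who are shown as unchanged:

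| Post-dose readings | Of those abnormal at baseline | Of all patients |
|---|---|---|
| 1 | 38% | about 14% |
| 3 | 15% | about 5.5% |
| 6 | 7% | about 2.7% |

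The columns agree within rounding: 0.375 × 0.38 ≈ 0.14, 0.375 × 0.15 ≈ 0.056, 0.375 × 0.07 ≈ 0.026. With a within-patient SD of 8, the first column becomes 32%, 12% and 6%.

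**The case against.** The best defence is that no sensible programmer would compare baseline with itself. The SAP computes change from post-baseline values, labels Cycle 1 Day 1 as Baseline in Table 4, and titles the tables as baseline against worst on-treatment. SAP 7.6 also refers to on-treatment flags and dataset specifications that are not in these documents and may already exclude the record. That is plausible, and it means the delivered tables need not be wrong. It does not rescue the text, because nothing quoted overrides the day-based period. The shells also point both ways: the hematology listing shows a change from baseline at C1D1, and the urinalysis shell gives C1D1 its own row after Baseline. Two programmers could produce different tables.

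The defence is right about consequences. The by-visit change tables 14.3-2.1, 14.3-2.4 and 14.3-3.1 and the laboratory and vital-sign listings are also kept for the final analysis. Improvements and absent post-dose data can be found there. The shift tables are descriptive, and TEAEs already carry the post-dose limit.

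Three stronger readings are tempting, and the documents do not support them:
- A reader might take the chance that baseline is the largest of k + 1 exchangeable values, 1/(k + 1), as the error rate: 25% at k = 3, 14% at k = 6. That applies to continuous values. In a categorical table a normal baseline with normal follow-up lands in the same cell under either rule.
- A reader might infer that pre-dose abnormality is presented as treatment-emergent. A 2-to-2 entry sits in the Grade 2 baseline row and reads as pre-existing.
- A reader might infer that all five tables are affected for everyone. Where laboratory screening falls within 72 hours before dosing, on a day before Day 1, and is not repeated on Day 1, there is no overlap.

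**Conclusion.** Wrong as written; minor severity. For any patient whose baseline is a Day 1 value, the stated rule makes improvement and Missing impossible in the shift tables, while worsening is captured correctly. The vital-sign table is affected for essentially all patients; the laboratory tables for an unknown fraction. The structural result rests only on the SAP's definitions. The systolic percentages rest on an assumed distribution with no drug effect and show the pattern only: the distortion is largest in patients with few post-dose assessments. No laboratory magnitude can be derived from the documents. No hypothesis test, efficacy endpoint or TEAE count changes.

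**What to change.** In SAP 7.3, 9.9.2 and 9.9.3.1, state that the worst on-treatment laboratory and vital-sign values are derived only from assessments after the first dose, by date and time. Untimed Day 1 assessments that the protocol plans before dosing are treated as pre-treatment. Exclude any record used as baseline from the worst-value derivation, and count patients with no qualifying value in the Missing column. Repeat the rule as a footnote to the five shift-table shells.

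The cost is one sentence in the SAP and one filter in the derivation. It brings these tables into line with the limit the SAP already sets for TEAEs, and I see no downside.
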